Clinical Trial Protocol

Document Number:		c21630258-01
EudraCT No.	2018-000057-41	
BI Trial No.	1402-0005	
BI Investigational Medicinal Product	BI 1358894	
Title	A double-blind, randomised, two-way cross-over, single-dose, placebo-controlled trial to investigate the effects of BI 1358894 on cholecystokinin tetrapeptide (CCK-4) induced panic symptoms in healthy male subjects	
Lay Title	A study in healthy men to test whether BI 1358894 reduces drug-induced panic symptoms	
Clinical Phase	I	
Trial Clinical Leader	Phone: _____ Fax: _____	
Principal Investigator	Phone: _____ Fax: _____	
Status	Final Protocol	
Version and Date	Version: 1.0	Date: 13 March 2019
Page 1 of 96		
Proprietary confidential information © 2019 Boehringer Ingelheim International GmbH or one or more of its affiliated companies. All rights reserved. This document may not - in full or in part - be passed on, reproduced, published or otherwise used without prior written permission		

Proprietary confidential information © 2019 Boehringer Ingelheim International GmbH or one or more of its affiliated companies

CLINICAL TRIAL PROTOCOL SYNOPSIS

Company name	Boehringer Ingelheim
Protocol date	13 March 2019
Revision date	Not applicable
BI trial number	1402-0005
Title of trial	A double-blind, randomised, two-way cross-over, single-dose, placebo-controlled trial to investigate the effects of BI 1358894 on cholecystokinin tetrapeptide (CCK-4) induced panic symptoms in healthy male subjects
Principal Investigator	
Trial site	
Clinical phase	I
Trial rationale	Inhibition of ion channels by BI 1358894 may potentially improve affective symptoms and emotion control in patients with affective disorders. The pharmacodynamic data obtained in this study will help to detect the pharmacological principle of the BI 1358894 compound by demonstrating indirect target engagement via downstream pharmacodynamic measures.
Trial objective	To investigate the pharmacodynamic effects of a single dose of BI 1358894 on CCK-4 induced anxiogenic/panic-like symptoms using the Panic Symptom Scale (PSS) in preselected CCK-4 sensitive healthy volunteers.
Trial design	Single dose, placebo-controlled, double-blind, randomised, two-way cross-over
Trial endpoint	Primary endpoint: maximum change from baseline of PSS sum intensity score after CCK-4 injection
Number of subjects	
total entered	20* *Screening may include more than 60 healthy subjects who will be exposed to CCK-4 to identify subjects with an anxiogenic and panic induced effect in response to CCK-4 as until 20 eligible subjects have been identified
each treatment	20 (all to receive both active treatment and placebo)
Diagnosis	Not applicable
Main criteria for inclusion	Healthy male CCK-4 sensitive subjects, age of 18 to 55 years (inclusive), body mass index (BMI) of 18.5 to 29.9 kg/m ² (inclusive)

Proprietary confidential information © 2019 Boehringer Ingelheim International GmbH or one or more of its affiliated companies

Challenging agent	CCK-4 (CCK B receptor agonist)
dose	50 µg
mode of admin.	iv bolus injection
Test product	BI 1358894 film-coated tablet, strength 25 mg (inhibitor)
dose	100 mg (4 film-coated tablets)
mode of admin.	Oral with 240 mL of water after a standard high-fat meal
Reference product	Matching placebo as film-coated tablet
dose	Not applicable
mode of admin.	Oral with 240 mL of water after a standard high-fat meal
Duration of treatment	2 single doses of CCK-4 and BI 1358894 or placebo (separated by a washout period of at least 17 days between drug administrations), 1 single dose of the provoking agent for the preselection of CCK-4 sensitive healthy subjects
Statistical methods	Descriptive statistics will be calculated for all endpoints. The statistical model to assess the primary pharmacodynamic endpoint PSS sum intensity score will be a mixed effects model including effects for 'treatment', 'period' and 'subject', as well as covariates 'period baseline' and 'subject baseline'. Two sided 90% confidence intervals (CIs) will be calculated based on the residual error from the mixed model.

Proprietary confidential information © 2019 Boehringer Ingelheim International GmbH or one or more of its affiliated companies

FLOW CHART FOR THE SINGLE DOSE CCK-4 CHALLENGE

Period	Visit	Day	Planned time (relative to drug administration [h:min])	Approximate clock time of actual day [h:min]	Event and comment	Safety laboratory	CCK-4 challenge ⁸	12-lead ECG	Continuous ECG monitoring	Vital signs (BP, PR)	Suicidality assessment ⁷	PSS/	Questioning for AEs and concomitant therapy ⁵
SCR	1	-28 to -7			Screening (SCR) ¹	x		x		x	x		
	2	-6 to -2	-0:15	08:00	Screening CCK-4-challenge visit ^{8,13}	x			▲	x		x	x
			0:00	08:15			x		—			x	
			0:05	08:20					—			x	
			0:10	08:25					—			x	
			0:20	08:35					—			x	
			0:30	08:45					▼			x	x ¹⁰
			4:45	13:00	lunch, discharge from trial site ¹⁴	x			x	x		x	x ¹⁰
two identical treatment periods separated by a wash-out of at least 17 days	3/4	1	-1	-18:00	14:00	Admission to trial site	x	x		x		x	x
			-2:00	06:00	allocation to treatment ²	x ^{2, 9}		x ²	▲	x ²			x ²
			-0:30	07:30	Breakfast								
			0:00	08:00	BI 1358894 drug administration or placebo				—			x ²	
			0:30	08:30		x		x		x			x
			1:00	09:00		x		x		x			x
			1:30	09:30		x							x
			2:00	10:00	240 mL fluid intake			x		x			x
			2:30	10:30		x							x
			3:00	11:00		x		x		x			x
			4:00	12:00	240 mL fluid intake ³	x		x	—			x	x
			4:30	12:30									
			4:45	12:45		x	x	x		x	x	x	x
			5:00	13:00	CCK-4 challenge ⁸		x						
			5:05	13:05		x						x	x ¹⁰
			5:10	13:10		x						x	x ¹⁰
			5:20	13:20		x						x	x ¹⁰
			5:30	13:30		x	x		—	x		x	x ¹⁰
			6:00	14:00	Lunch ³	x	x	x	▼	x			x ¹⁰
			7:00	15:00		x	x						
			8:00	16:00	Snack (voluntary) ³	x	x	x		x			
			10:00	18:00	Dinner ³	x	x						
			12:00	20:00		x		x		x			
		2	24:00	08:00		x	x	x		x			x ¹⁰
			34:00	18:00		x		x		x			x
		3	48:00	08:00		x		x		x			x
		4	72:00	08:00		x		x		x			x

Proprietary confidential information © 2019 Boehringer Ingelheim International GmbH or one or more of its affiliated companies

		5	96:00	08:00			x	x			x		x				x
		6	120:00	08:00				x			x		x				x
		7	144:00	08:00				x			x		x				x
		8	168:00	08:00				x			x		x				x ¹⁰
		9	192:00	08:00	Discharge from trial site ¹¹		x	x			x		x	x	x	x	x
		13	288:00	08:00	Ambulatory visit ¹²			x									
EOT	5	35 to 40			End of trial (EOT) examination ⁴		x				x		x	x	x	x	x

1. Subject must be informed and written informed consent obtained prior to starting any screening procedures. Screening procedures include physical examination, check of vital signs, ECG (including rhythm strip of at least 10 sec), safety laboratory (including drug screening and alcohol urine test), demographics (including determination of body height and weight, smoking status and alcohol history), neurological examination, relevant medical history, concomitant therapy, review of inclusion/exclusion criteria and suicidality assessment (C-SSRS).
2. The time is approximate; the respective procedure is to be performed and completed within 3 h prior to drug administration. Allocation to treatment may be performed at any time following enrolment but must be completed prior to (first) drug administration.
3. If several actions are indicated at the same time point, the intake of meals will be the last action.
4. End of trial examination includes physical examination, body weight, vital signs, ECG, safety laboratory, recording of AEs, concomitant therapies, suicidality assessment (C-SSRS), neurological examination, and PSS
5. AEs and concomitant therapies will be recorded throughout the trial, but will be specifically asked for at the time points indicated in the [Flow Chart](#) above.
6. Sampling times and periods may be adapted based on information obtained during the trial including addition of samples and visits as long as the total blood volume taken does not exceed 500 mL per subject
7. Suicidality assessment only at screening, admission to trial site, discharge from trial site and end of trial.
8. CCK-4 challenge test (CCK-4 injection (50 µg)) is to be performed after subjects have had a standard high-fat meal except Visit 2, no breakfast is needed at Visit 2. Injection time must be recorded. PSS assessments will be determined 5 ± 1 , 10 ± 1 , 20 ± 1 and 30 ± 1 minutes after the injection. The CCK-4 will be administered to the subjects as a bolus injection over 5 seconds (maximum of 8 seconds) via a venous cannula.
9. One additional blood sample for pharmacogenomics analyses will be taken either at Visit 3 or at Visit 4.
10. Standardized assessment of local tolerability using the criteria swelling, induration, heat, redness, pain or other findings.
11. Discharge on Day 9 includes physical examination, vital signs, ECG, safety laboratory, recording of AEs, concomitant therapies, suicidality assessment (C-SSRS), PSS and a neurological examination.
12. For ambulatory visit examinations, a time window of 3 hours is acceptable.
13. The time is approximate and could start between 8:00 to 12:00
14. Discharge after screening CCK-4 challenge after confirmation of fitness by PI or designee

TABLE OF CONTENTS

TITLE PAGE	1
CLINICAL TRIAL PROTOCOL SYNOPSIS	2
FLOW CHART FOR THE SINGLE DOSE CCK-4	
CHALLENGE	4
TABLE OF CONTENTS	6
ABBREVIATIONS	11
1. INTRODUCTION.....	14
1.1 MEDICAL BACKGROUND.....	14
1.2 DRUG PROFILE	15
1.2.1 BI 1358894	15
1.2.1.1 Nonclinical pharmacology	15
1.2.1.2 Safety pharmacology	15
1.2.1.3 Toxicology	16
1.2.1.3.1 Single dose toxicity	16
1.2.1.3.2 Repeat-dose toxicity studies.....	17
1.2.1.3.3 Genotoxicity	19
1.2.1.3.4 Reproductive and developmental toxicity.....	19
1.2.1.3.5 Phototoxicity	19
1.2.1.4 Nonclinical pharmacokinetics.....	19
1.2.1.5 Clinical experience in humans	21
1.2.1.6 Drug product	28

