1.4.1 Procedure-related risks

The use of an indwelling venous catheter or venepuncture for e.g. blood sampling may result in mild bruising, and in rare cases, in transient inflammation of the wall of the vein, or nerve injury, potentially resulting in paraesthesia, reduced sensibility, and/or pain for an indefinite period.

The total volume of blood withdrawn per subject during the entire study will not exceed the volume of a normal blood donation (500 mL). No health-related risk to healthy subjects is expected from withdrawal of this volume of blood.

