2.2.2.3 Local tolerability

Local tolerability of CCK-4 injections will be assessed by the investigator or designee on the basis of swelling, induration, heat, redness, pain, and other findings.

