5.3.3 Safety and Tolerability endpoints

Safety and tolerability of BI 1358894 will be assessed based on parameters defined in Section 2.2.2.2 and Section 2.2.2.3 of the CTP:

- *Adverse events (including clinically relevant findings from the physical and neurological examinations)*
- *Safety laboratory tests*
- *12-lead ECG*
- *Continuous ECG monitoring*
- *Vital signs (blood pressure, pulse rate)*
- *Suicidality assessment (C-SSRS)*

Local tolerability of CCK-4 injections (absence or presence of "swelling", "induration", "heat", "redness", "pain", or "other findings") will be summarized with counts and percentages overall (i.e. subject-wise worst case over all injections and time points) as well as listed by injection and time point.

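### No local tolerability inspection is scheduled before any of the three CCK-4 injections, so a cannula-site sign already present and still visible afterwards would enter the SAP's worst-case count (minor)

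*Protocol*

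**What the plan says.** Section 2.2.2.3 of the protocol sets the aim: "Local tolerability of CCK-4 injections will be assessed by the investigator or designee on the basis of swelling, induration, heat, redness, pain, and other findings". Section 5.2.5.1 repeats the criteria and adds nothing on timing.

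Timing comes from the Flow Chart, through footnote 10: "Standardized assessment of local tolerability using the criteria swelling, induration, heat, redness, pain or other findings". At Visit 2 the injection is at 0:00 and the footnote is attached to 0:30 and 4:45. At Visits 3 and 4 the injection is at 5:00 and the footnote is attached to 5:05, 5:10, 5:20, 5:30, 6:00, 24:00 and 168:00. The last rows before the injection (-0:15 at Visit 2, 4:45 at Visits 3/4) show adverse event questioning without footnote 10.

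Footnote 8 says that CCK-4 is "administered to the subjects as a bolus injection over 5 seconds (maximum of 8 seconds) via a venous cannula". Section 1.4.1 names the risk of the access itself: "The use of an indwelling venous catheter or venepuncture for e.g. blood sampling may result in mild bruising, and in rare cases, in transient inflammation".

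For the analysis, SAP 5.3.3 records each sign as absent or present and reports it "overall (i.e. subject-wise worst case over all injections and time points) as well as listed by injection and time point".

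**The concern.** The summary is labelled as the local tolerability of the CCK-4 injections, but the cannula is in place before CCK-4 is given and the protocol accepts that a catheter can itself cause local reactions. With no inspection beforehand, a sign already present is recorded for the first time after the injection and looks the same as a new one. The worst-case rule then needs only one such sign, at any of three injections, to count the subject.

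No comparison elsewhere in the plan separates the two causes. CCK-4 is given at screening and in both treatment periods, and no vehicle injection is planned. The listing by injection and time point also starts after the injection. SAP 6.7 does define baseline as the last available value before the CCK-4 challenge in the period, but for local tolerability no such value is scheduled, so that definition has nothing to work on.

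At stake is how a descriptive safety table is read, and nothing beyond that.

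**Working it through.** The documents give no figure for local tolerability, so there is none to reproduce. The check is a count of the schedule followed by an illustration.

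**Count of inspections (Flow Chart, footnote 10)**

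| Visit | Injection | Marked inspections, as time after injection | Number | Before injection |
|---|---|---|---|---|
| 2 | 0:00 | 30 min, 4 h 45 min | 2 | 0 |
| 3 | 5:00 | 5, 10, 20, 30, 60 min; 19 h; 163 h | 7 | 0 |
| 4 | 5:00 | same as Visit 3 | 7 | 0 |

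Total per subject: 2 + 7 + 7 = 16, of which 0 precede an injection.

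**Path of a pre-existing sign.** The sign is present before the injection (no inspection), is still visible at a later marked time (recorded as present), and enters the subject's worst case (SAP 5.3.3). Nothing in SAP 5.3.3 asks whether it was there before.

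**Illustration of size.** Inputs from the documents: 3 injections per subject (protocol 4.1.1) and 20 subjects (protocol 7.7). Assumed: a chance q per injection that a cannula-site sign is present beforehand and persists to a marked inspection; independence across injections; and no sign caused by CCK-4 itself.

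Share of subjects counted = 1 - (1 - q)^3

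- q = 2%: 1 - 0.98^3 = 1 - 0.941 = 5.9%, or 20 × 0.059 = about 1.2 subjects
- q = 5%: 1 - 0.95^3 = 1 - 0.857 = 14.3%, or 20 × 0.143 = about 2.9 subjects

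Independence matters. If the same subjects reacted to the cannula every time, the share would stay at q itself: 2% to 5%, or 0.4 to 1 of 20 subjects.

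**The case against.** The other side has a good deal that stands.

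- **Tolerability may include the procedure.** Neither document says that CCK-4 caused each sign, and a worst-case summary is a familiar cautious convention; SAP 6.7 also uses worst values for laboratory data. This is fair, and it is one reason to keep the all-signs count. The reader still cannot tell what was new after the injection.
- **There is a partial safeguard.** Adverse events are recorded throughout with onset times, and subjects are questioned just before each injection. A painful site reported then would carry an earlier onset, which could be read beside the listing. But this questioning is non-specific, is not an inspection of the site, and is not linked to the summary.
- **The consequence is small.** CCK-4 is a non-investigational agent, the safety analysis is descriptive, and no eligibility or stopping rule rests on this table. This stands in full.

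A reader might also infer more than the documents support:

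- *That the summary can only overstate local reactions.* The schedule can also miss some. At Visit 2 the first inspection is 30 minutes after the injection, and in the treatment periods none is marked between 6:00 and 24:00.
- *That an earlier look would fully separate CCK-4 from the cannula.* It identifies only signs already present. Signs from the cannula or from later blood draws that first appear after the injection would remain mixed in.
- *That blood-draw reactions at the same site are counted.* The sample collection text is not visible, so whether the cannula or arm is shared is unknown. The cannula argument does not depend on it.
- *That large numbers of subjects are affected.* Section 1.4.1 calls vein inflammation rare, and bruising is not one of the five named signs. Nothing in the documents anchors a high value of q.

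**Conclusion.** The point holds as a minor one. It rests on two facts in the text: no standardised inspection precedes any of the three injections, and the worst-case summary in SAP 5.3.3 has no baseline. It follows that a cannula-site sign which was present before the injection and persisted would be counted. It does not follow that such signs will occur, and their frequency is not given. The figure of about 6% to 14% of subjects is conditional on an assumed 2% to 5% per injection, independence across injections, persistence to a marked inspection, and no true CCK-4 effect; it shows how pooling three injections acts and is not a forecast. The primary endpoint and the comparison of BI 1358894 with placebo are unaffected.

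**What to change.** **Flow Chart:** add footnote 10 to the -0:15 row at Visit 2 and to the 4:45 row at Visits 3/4. PSS, vital signs and adverse event questioning already take place at those rows.

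**SAP 5.3.3:** keep the all-signs worst-case count. Beside it, show the worst-case count restricted to signs that were absent at the pre-injection look for the same injection. Flag pre-existing signs in the listing.

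**Cost:** three short inspections and three form entries per subject, with no added visit, plus a short addition to SAP 5.3.3. The schedule change must be in place before the injections it is meant to cover, since an inspection not made cannot be recovered later.

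**Limits:** because signs are recorded only as absent or present, a pre-existing sign that worsens would appear only in the all-signs count and the listing unless a grade were added. Cannula or venepuncture signs that first appear after the injection would still not be separated from CCK-4.

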Proprietary confidential information © 2019 Boehringer Ingelheim International GmbH or one or more of its affiliated companies

8.5.1	Collection, storage and future use of biological samples and corresponding data	78
8.6	TRIAL MILESTONES	78
8.7	ADMINISTRATIVE STRUCTURE OF THE TRIAL	79
9.	REFERENCES	80
9.1	PUBLISHED REFERENCES.....	80
9.2	UNPUBLISHED REFERENCES.....	82
10.	APPENDICES	84
10.1	PREPARATION INSTRUCTIONS FOR CCK-4	84
10.2	COLUMBA-SUICIDE SEVERITY RATING SCALE	85
10.4	PANIC SYMPTOM SCALE.....	92
11.	DESCRIPTION OF GLOBAL AMENDMENT(S)	95
11.1	GLOBAL AMENDMENT 1	95
11.2	GLOBAL AMENDMENT 2	95

ABBREVIATIONS

ADME	Absorption, distribution, metabolism, and excretion
AE	Adverse event
AESI	Adverse events of special interest
ALT	Alanine amino transferase
AST	Aspartate amino transferase
AUC $0-\infty$	Area under the concentration-time curve of the analyte in plasma over the time interval from 0 extrapolated to infinity
AUC $5-5.5$	area under the concentration-time curve of the analyte in plasma over the time interval 5h to 5:30h
AUC $0-24$	Area under the concentration-time curve of the analyte in plasma during 24 hours
AUC $0-72$	Area under the concentration-time curve of the analyte in plasma during 72 hours
AUC $0-tz$	Area under the concentration-time curve of the analyte in plasma over the time interval from 0 to the last quantifiable data point
BA	Bioavailability
BI	Boehringer Ingelheim
BMI	Body mass index (weight divided by height squared)
BP	Blood pressure
BPD	borderline personality disorder
b.p.m.	Beats per minute
CA	Competent authority
CCK-4	Cholecystokinin tetrapeptide
CHO	Chinese hamster ovary
CI	Confidence interval
Cmax	Maximum measured concentration of the analyte in plasma
CNS	Central Nervous System
CRF	Case report form
CRO	Clinical Research Organization
C-SSRS	Columbia-Suicide Severity Rating Scale
CTM	Clinical Trial Manager
CTP	Clinical trial protocol
CTR	Clinical trial report
CV	Arithmetic coefficient of variation
CYP	Cytochrome P450
DILI	Drug induced liver injury

Proprietary confidential information © 2019 Boehringer Ingelheim International GmbH or one or more of its affiliated companies

DNA	Desoxyribonucleic acid
DRF	Dose Range Finding
ECG	Electrocardiogram
eCRF	Electronic case report form
ECT	electro-convulsive therapy
eDC	Electronic data capture
EDTA	Ethylenediaminetetraacetic acid
E_{\max}	maximum PSS sum intensity score after CCK-4
EOT	End of trial
ES	Entered Set
ESR	Erythrocyte sedimentation rate
EU	European Union
FDA	Food and Drug Administration
FE	Food Effect
FIH	First in Human
FST	Forced Swim Test
GCP	Good Clinical Practice
gCV	Geometric coefficient of variation
gMean	Geometric mean
hERG	human ether-a-go-go related gene
HIV	Human Immunodeficiency Virus
IB	Investigator's brochure
ICH	International Conference of Harmonisation
IEC	Independent Ethics Committee
IPD	Important Protocol Deviation
IRB	Institutional Review Board
ISF	Investigator site file
IUD	Intrauterine device
i.v.	Intravenous
LVSP	left ventricular pressure parameters
MDA	Methylenedioxymethamphetamine
MDD	Major depressive disorder
MDMA	Methylenedioxymethamphetamine
MedDRA	Medical Dictionary for Regulatory Activities
MRT_{po}	Mean residence time of the analyte in the body after oral administration
NIMP	Non-investigational medicinal product
nM	Nanomolar

Proprietary confidential information © 2019 Boehringer Ingelheim International GmbH or one or more of its affiliated companies

NOAEL	No observed adverse effect level
PD	Pharmacodynamic(s)
PK	Pharmacokinetic(s)
PKS	Pharmacokinetic set
p.o.	Oral
PR	Pulse rate
PSS	Panic Symptom Scale
q.d.	Quaque die , once daily
QD	Once Daily
QT	Time between start of the Q-wave and the end of the T-wave in an electrocardiogram
QTc	QT interval corrected for heart rate using the method of Fridericia (QTcF) or Bazett (QTcB)
R	Reference treatment
REP	Residual effect period
SAE	Serious adverse event
SCR	Screening
SRD	Single-rising dose
Ss	(at) steady state
SOP	Standard Operating Procedure
T	Test product or treatment
TMF	Trial master file
t_{\max}	Time from (last) dosing to the maximum measured concentration of the analyte in plasma
$t_{1/2}$	Terminal half-life of the analyte in plasma
t_z	Time of last measurable concentration of the analyte in plasma
TSAP	Trial statistical analysis plan
ULN	Upper limit of normal
VAS	Visual Analogue Scale
WBC	White Blood Cells

Proprietary confidential information © 2019 Boehringer Ingelheim International GmbH or one or more of its affiliated companies

1. INTRODUCTION

1.1 MEDICAL BACKGROUND

1.2 DRUG PROFILE

1.2.1 BI 135894

1.2.1.1 Nonclinical pharmacology

1.2.1.2 Safety pharmacology

1.2.1.3 Toxicology

1.2.1.3.1 Single dose toxicity

Proprietary confidential information © 2019 Boehringer Ingelheim International GmbH or one or more of its affiliated companies

1.2.1.3.2 Repeat-dose toxicity studies

1.2.1.3.3 Genotoxicity

1.2.1.3.4 Reproductive and developmental toxicity

1.2.1.3.5 Phototoxicity

1.2.1.4 Nonclinical pharmacokinetics

1.2.1.5 Clinical experience in humans

Proprietary confidential information © 2019 Boehringer Ingelheim International GmbH or one or more of its affiliated companies

Pharmacokinetics

